I agree to conduct this study in full compliance with INS Regulations, DIGEMID, Institutional Review Board/Ethics Committee Regulations and the International Conference on Harmonization of Good Clinical Practice Guidelines.

Investigator's Name

Investigator's Signature

Date:

Near Infrared Transcranial Laser Therapy in Subjects with Major Depressive Disorder: A study of Dosing with Laser.

SUMMARY TABLE OF CHANGES TO PROTOCOL AMENDMENT version 5.1 dated December 17, 2023

JUSTIFICATION: Amendment 5.1 is proposed due to typographical errors observed in official communication No. 1046-2023-DIIS/INS dated October 31, 2023.

Nº	It said	It should say	Justification of the change	References
1	
In section 1. Study Summary: (...) All NIR-TLT sessions will be 20 minutes, regardless of group assignment (...).
 
In section 3.2 Lite Cure Laser System Overview: (...) the treatment time will be the same in all modes: 20 minutes.
 
In Section 4.4 Study Design: (...) The entire session is estimated to last 30 minutes (...)
 
In section 4.8.2 Treatment Visits 1 to 18- Visits 1-6: (...) Treatment visits are estimated to last approximately 20 minutes-(...)
	
In section 1. Summary of the Study: All NIR-TLT sessions will be 429 seconds (7.15 minutes), regardless of group assignment.
 
In section 3.2 Lite Cure Laser System Overview: (...) the treatment time will be the same in all modes: 429 seconds (7.15 minutes).
 
In section 4.4 Study Design: (...) The entire session is estimated to last (which includes the 429-second treatment and all procedures described in the "Study Visits" section) 30 minutes (...)
 
In section 4.8.2 Treatment Visits 1 to 18 - Visits 1-6: (...) It is estimated that treatment visits will last approximately 429 seconds (7.15 minutes) (...)
	
It is being standardized to 429 seconds (7.15 minutes) in all sections to standardize the amendment.
	N.A.

Near Infrared Transcranial Laser Therapy in Subjects with Major Depressive Disorder: A study of Dosing with Laser.

2	
In section 5.1 General Considerations: (...) 120 patients were included, randomly distributed in five groups. (...)
 
(...) The purpose of this study is to compare the antidepressant effect of five different doses of NIR-TLT (...)
 
In section 5.2 Objectives of the study: (...) To compare the effect(s) of each of the five doses of NIR-TLT (...)
	
In section 5.1 General Considerations: (...) 112 patients were included, randomly distributed in four groups. (...)
 
(...) The purpose of this study is to compare the antidepressant effect of four different doses of NIR-TLT (...)
 
In section 5.2 Study objectives: (...) To compare the effect(s) of each of the four doses of NIR-TLT (...)
	
The arm that was to receive the NIR-TLT dose is eliminated: Mode 4 (UPW Group). The number of patients for the study is corrected.
	N.A.
3	
In the paragraphs of the document referring to the name of the sponsor, it has been changed.
 
Formerly as: Lite Cure LLC
	
In the paragraphs of the document referring to the name of the sponsor, it has been changed.
 
Now it should say: Pthera LLC
	
Due to the change in the sponsor of the study, the change was made to standardize the information in the document.
	N.A.
Nº	OTHER CHANGES			
1	NOT APPLICABLE			

Near Infrared Transcranial Laser Therapy in Subjects with Major Depressive Disorder: A study of Dosing with Laser.

1. Summary of the Study

Objectives of the Study:	
The objectives of this study are:
 
Primary:
 
• A. To evaluate and compare the effect(s) of each of the four doses of NIR-TLT on depressive symptomatology: antidepressant effect, in patients with major depressive disorder (MDD). 
Secondary:
 
• B. Compare safety and tolerability at each dose of NIR-TLT.• C. Compare the effect(s) of each of the four doses of NIR-TLT on brain electrophysiology. 
Exploratory:
 
• D. To describe the findings visualized in PET, related to the brain metabolism of the participants, before and after receiving the intervention under study.
Study Design:	
Multi-center, randomized, sham, double-blind.
 
This trial will randomize 112 subjects into 4 equal groups: bilateral continuous wave (BCW), bilateral pulsed wave (BPW 1-2) and SHAM. All subjects, investigators (except the study statistician) and outcome assessors will be blinded to group assignments. The device operator will be aware of group assignments.
 
All subjects will receive 3 NIR-TLT sessions per week for 6 weeks. A follow-up evaluation will be performed 2 weeks after the end of the study. The treatment will follow these specifications: wavelength 830 nm; average irradiance 54.8 mW / cm²; average fluence of 65.8 J / cm² (according to the parameters used in the ELATED-2 study at MGH with the Omnilux New U device), being the total fluence delivered: 3.6 kJ (bilateral) or 1.8 kJ (unilateral), either on the subject's forehead, at or near the electroencephalography (EEG) sites F3 and F4.
 
All NIR-TLT sessions will be 429 seconds (7.15 minutes), regardless of group assignment.

Study population:	
Patients eligible to participate in the study will be diagnosed with MDD by DSM criteria (MINI). Subjects will be between 18 and 75 years of age (not yet 76 years of age) on the date of the examination.

Duration of participation:	
Research subjects will remain in the study for 8 weeks. (6-week treatment period, plus 2-week follow-up). The total duration of the study will be 24 months.

Near Infrared Transcranial Laser Therapy in Subjects with Major Depressive Disorder: A study of Dosing with Laser.

Criteria for valuation:

- **Main:** Improvement of depressive symptoms from each of the four doses of NIR-TLT. Assessed using HAMD-17, at 3 time points (visit 1, visit 9 and visit 18).
- **Secondary:** Safety and tolerability. Assessed by SAFTEE- SI (self-assessed), and collection of serious adverse events throughout the study. Safety data will be used to assess the tolerability of each of the NIR-TLT doses.
Changes in brain electrophysiology (electrical activity): Commercially available EEG devices will be used to collect data on brain electrical activity. At 3 time points (visit 1, visit 9 and visit 18).
- Changes in measurements of MDD symptom severity assessment scales:
 - Doctor Administered Scales: QIDS-C and CGI-S
 - Patient-reported scales: ASQ and SDQ

Entry Criteria:

Inclusion Criteria

1. The age of the subjects in the examination will be between 18 and 75 years (inclusive).
2. Diagnosis of major depressive disorder (MINI).
3. QIDS-C \geq 12 in the selection
4. CGI-S \geq 4 or greater, i.e., "moderately depressed".
5. Women of childbearing age should use a double-barrier method of birth control (e.g., condoms plus spermicides) if they are sexually active.
6. Subject's informed consent obtained in writing in accordance with local regulations prior to enrollment in this study.
7. The subject is willing to participate in this study for at least 12 weeks.
8. Subjects should receive stable doses of antidepressants (if taking any) afor at least six weeks prior to enrollment.

Exclusion Criteria:

1. Decrease in SDQ self-reporting from screening to initiation.
 $\geq=30\%$, calculated as $[(SDQ_{selection}-88) - (SDQ_{initial}-88)] / (SDQ_{selection}-88)] \geq=30/100$. A score of 88 is "normal" in SDQ.
2. Subject is pregnant or breastfeeding.

Near Infrared Transcranial Laser Therapy in Subjects with Major Depressive Disorder: A study of Dosing with Laser.

3. Subject failed more than 2 adequate FDA-approved antidepressant treatments during the current episode according to ATRQ criteria (less than 50% decrease in depressive symptomatology).
4. Structured psychotherapy focused on treating the subject's depression (i.e., CBT or IPT) is allowed if initiated at least 8 weeks prior to the screening visit.
5. Substance dependence or abuse in the last 3 months.
6. History of a psychotic disorder or psychotic episode (current psychotic episode by MINI assessment).
7. Bipolar affective disorder (according to MINI evaluation).
8. Unstable medical illness, defined as any medical illness that is not well controlled with standard of care medications (e.g., insulin for diabetes mellitus, HCTZ for hypertension).
9. Active suicidal or homicidal ideation (both intent and plan are present), as determined by C-SSRS screening.
10. The subject has a significant skin condition (i.e., hemangioma, scleroderma, psoriasis, rash, open wound, or tattoo) on the subject's scalp that is in close proximity to any of the procedure sites.
11. Subject has an implant of any type in the head (e.g., stent, clipped aneurysm, embolized AVM, implantable shunt - Hakim valve).
12. Any use of light-activated medications (photodynamic therapy) within 14 days prior to study enrollment (in the U.S .Visudin (verteporfin) - for age-related macular degeneration; Aminolevulinic acid - for actinic keratoses; Photofrin (sodium porfimer) - for esophageal cancer, non-small cell lung cancer; Levulan Kerastick (aminolevulinic acid HCl) - for actinic keratoses; 5-aminolevulinic acid (ALA) - for nonmelanoma skin cancer)
13. Recent history of stroke (90 days).
14. Subject had a failed intervention based on an FDA-approved device for the treatment of depression, during the current episode (e.g., less than 50% decrease in depressive symptomatology with TMS, ECT, or VNS).
15. History of dementia, traumatic brain injury (TBI) or other organic neurological disorder.

Near Infrared Transcranial Laser Therapy in Subjects with Major Depressive Disorder: A study of Dosing with Laser.

2. List of Abbreviations

ANCOVA = Analysis of Covariance
ANOVA = Analysis of Variance
ASQ = Anxiety Symptom Questionnaire
ATP = Adenosine Triphosphate
BOLD fMRI = blood-oxygen level dependent functional magnetic resonance imaging
C-SSRS = Columbia Suicide Severity Rating Scale
CFR = Code of Federal Regulations
CGI-I = Clinical Global Impressions: Improvement
CGI-S = Clinical Global Impressions: Severity
CRF= Case Report Form
CW = Continuous Wave
DNA = Deoxyribonucleic acid
DSMB = Data and Safety Monitoring Board
ECT= Electroconvulsive Therapy
ETC= Electron Transport Chain
FDA= Food and Drug Administration
HAM-D-17 = Hamilton Depression Rating Scale
HCTZ = Hydrochlorothiazide
ISO = International Standards Organization
MDD = Major depressive disorder
MINI= Mini-International Neuropsychiatric Interview
NEST 1 = NTS® Effectiveness and Safety Trial - 1
NEST 2 = NTS® Effectiveness and Safety Trial - 2
NIMH = National Institute of Mental Health
NIR-TLT = Near-infrared Transcranial Laser Therapy
OSHA = Occupational Safety & Health Administration
PBM = Photobiomodulation
PET *scan* / PET: Positron Emission Tomography
PI = Principal Investigator at the center
QIDS-CR = Quick Inventory of Depressive Symptomatology: Doctor-rated scale
RA = Research associate
SAE = Serious Adverse Events
SAFTEE-SI = Systematic Assessment for Treatment Emergent Effects
SCID = Structured Clinical Interview for DSM disorders
SQL = Structured Query Language
SSRI = Selective serotonin reuptake inhibitor
t-PBM = Transcranial photobiomodulation
TLT = Transcranial Laser Therapy
TMS = Transcranial Magnetic Stimulation
VNS= Vagus Nerve Stimulation

Near Infrared Transcranial Laser Therapy in Subjects with Major Depressive Disorder: A study of Dosing with Laser.

3. Introduction

Major depressive disorder (MDD) is a prevalent and disabling condition: 16.2% of the U.S. population has MDD at some point in life (Kessler et al., 2003). In the United States, depression is the third leading cause of years lost to disability or death, after cardiovascular disease and lung and breast cancer (Michaud et al., 2006). Despite the availability of effective treatments such as antidepressants and psychotherapy, MDD often remains untreated, with only one-fifth of cases receiving adequate treatment (Kessler et al., 2003). In addition, diagnosis and treatment rates for depression among Blacks and Hispanics are less than half the rates observed for Whites (Sclar et al., 2008). Hispanics and Blacks have far more concerns regarding the effects of medications on quality of life than Whites (Huang et al., 2009). Among Hispanics, the stigma associated with receiving antidepressants is a major concern (Interian et al., 2007). Delayed treatment for depression not only prolongs associated disability, but may result in lower rates of response to antidepressants (de Diego-Adelino et al., 2009).

The current standard treatments for MDD are antidepressants and psychotherapy. Antidepressants are effective, but their efficacy is often limited by treatment adherence (Lingam and Scott, 2002). Psychosocial interventions are generally preferred in primary care (Backenstrass et al., 2006), especially among minorities (Givens et al., 2007), but are generally not cost-effective due to the higher upfront costs of providing psychotherapy (Barrett et al., 2005). In addition, counseling and psychotherapy are limited in the community because of the lack of counselors who are culturally trained and fluent in specific languages (e.g., Spanish).

Due to the limitations of drug treatment and talk therapy, new treatment approaches for depression are needed, especially in primary care and in the community, where several minorities are underserved. We propose a new treatment approach for depression based on the use of transcranial laser therapy (TLT). The treatment consists of bilaterally exposing the forebrain to TLT, which can enhance ATP production in depressed subjects.

Major depressive disorder has been associated with deficits in brain bioenergetic metabolism. In an experimental model of depression, chronic stress inhibited the mitochondrial respiratory chain (the cellular site for energy production) (Rezin et al., 2008). Depressed subjects also have significantly lower production of ATP (an energy vector) in their muscle tissue and a higher incidence of deletions in their mitochondrial DNA (Gardner et al., 2003). Magnetic resonance spectroscopy data in subjects with MDD showed that the response to augmentation of a selective serotonin reuptake inhibitor (SSRI) with triiodothyronine (a thyroid hormone) is associated with restoration of ATP levels in the brain (Iosifescu et al., 2008).

Near infrared light is a non-ionizing electromagnetic wave, is invisible, penetrates the skin and skull into brain tissue, is non-invasive (Zhang et al., 2000), dissipates minimally as thermal energy and is absorbed mainly by specific chromophores (Mochizuki-Oda et al., 2002). The benefits of NIR-TLT are wavelength specific. A mitochondrial enzyme, cytochrome c oxidase, is the primary chromophore for NIR-TLT with a wavelength of about 830 nm (Eells et al., 2003). The energy absorbed by cytochrome c oxidase leads to increased production of adenosine triphosphate (ATP) through the respiratory chain. Ultimately, the increase in ATP leads to an increase in the cell's energy metabolism, and presumably also activates a signaling cascade that promotes cell plasticity and cytoprotection. (Eells et al., 2003).

Near Infrared Transcranial Laser Therapy in Subjects with Major Depressive Disorder: A study of Dosing with Laser.

These properties of NIR-TLT have led to new therapeutic applications in neurology. In subjects with acute ischemic stroke, acute treatment with NIR-TLT led to a significantly better outcome compared to sham treatment (Lampl et al., 2007). These results were confirmed in a different cohort of stroke patients with mild to moderate disease severity (Zivin et al., 2009). Both studies in stroke subjects showed no significant difference in the rate of adverse events or serious adverse events between NIR-TLT and sham-treated subjects (Lampl et al., 2007; Zivin et al., 2009). NIR-TLT has also been used as a treatment for alopecia (Leavitt et al., 2009) and in animal models for methanol-induced retinal toxicity (Eells et al., 2003). Near-infrared light is already widely used for noninvasive assessment of brain function (replacing fMRI in studies of infants and young adults, under the name of Near Infrared Spectroscopy), underscoring the relatively low risk of NIR-TLT. The greatest risk of NIR-TLT when using a laser as a light source is associated with accidental exposure of the retina, when beams are projected through the lens, which increases the risk of macular injury (Kim et al., 2007). In our study, we will have multiple safeguards against this risk [See Section 4.9, Completion].

Preliminary uncontrolled studies in 10 and 4 depressed subjects, respectively, have shown NIR-TLT to be safe, effective and well tolerated (Schiffer et al., 2009; Cassano et al., 2015). Our study offers a larger sample size, a cleaner design with placebo control (also called sham treatment) and tests the efficacy and tolerability of repeated sessions of NIR-TLT. Because NIR-TLT is non-ionizing radiation, multiple sessions, likely necessary for the treatment of depression, are expected to be safe.

The advantage of the NIR-TLT treatment approach over pharmacotherapy is that adherence can be easily monitored (since the treatment is administered in the clinic) and the patient is not required to ingest any substances. It is possible that exposure to NIR-TLT is more acceptable than medication use among some minorities. Compared to talk therapy, NIR-TLT has the advantage of not requiring providers with specific cultural expertise or proficiency in a second language. Our study will help determine whether NIR-TLT has an antidepressant effect and is acceptable in minority populations, thus justifying further study and investment.

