The NIR-TLT delivery is expected to last no longer than 7.15 minutes (429 seconds) in total (simultaneous application to the left and right forehead). The subject will be allowed to rest for 5 minutes after NIR-TLT delivery. The skin at the application sites will be inspected again after laser application. A log will be kept with the dates of delivery of the NIR-TLT.

Near Infrared Transcranial Laser Therapy in Subjects with Major Depressive Disorder: A study of Dosing with Laser.

treatment per study subject. The use of cell phones, tablets, computers or electronic devices will not be allowed during laser administration.

[figure not shown]
During treatment visits and prior to NIR-TLT, study personnel will collect tolerability (safety) and efficacy data:

1. Safety data: SAFTEE-SI (self-assessed), C-SSRS, adverse events and concomitant medication form.
2. Efficacy data - HAMD-17.

In addition to the evaluation described above, during visits 1, 9 and 18:

Prior to the NIR-TLT study, the staff will collect primary efficacy data from metric measurements and brain electrophysiology data:

1. Efficiency data:
 - a. Doctor-administered scales (1): HAMD-17, QIDS-C and CGI-S.
 - b. Patient-Reported Scales (1): ASQ and SDQ
2. Brain Electrophysiology Data - Study personnel will conduct a first 10-minute EEG recording session, treat the patient according to their NIR-TLT group randomization, and then conduct a second 10-minute EEG recording session as soon as possible after the end of treatment, but within 15 minutes.

3. Exploratory PET scan data: A PET scan will be performed on the participants selected to be part of the research subgroup, before the first treatment visit and within 24 hours of the end of the last intervention (visit 18).

4.9.3 Follow-up visit (Post Treatments) - Week 8

Near Infrared Transcranial Laser Therapy in Subjects with Major Depressive Disorder: A study of Dosing with Laser.

The next visit will occur two weeks after the last cerebral blood flow impact visit.

Purpose: The purpose of the follow-up visit is to evaluate the long-term antidepressant effect of NIR-TLT.

Procedures: During the follow-up study, staff will collect tolerability (safety) and efficacy data:

1. Safety data: SAFTEE-SI (self-assessed), adverse events and concomitant medication form.

2. Efficiency data:

- a. Doctor-administered scales (1): HAMD-17, QIDS-C and CGI.
- b. Patient-reported scales (1): SDQ and ASQ.

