4.9.4 Completion

If, during the study, a subject's CGI-S increases more than 2 points or rises above a score of 5, or if they become actively suicidal according to the C-SSRS scale, the subject will be referred to their treating doctor and advised to start or switch to another FDA-approved antidepressant medication. Such subjects may or may not be terminated from the study, depending on the severity of symptoms, at the clinical judgment of the principal investigator. Subjects who are considered actively suicidal and in imminent danger will be terminated from the study and referred to the appropriate local MGH or NKI emergency room for evaluation and subsequent hospitalization, or, if the subject is appropriate for outpatient monitoring, will be referred to their treating doctor for frequent appointments and follow-up. Each subject will have the investigator's contact information, as well as instructions on how to call emergency services, if necessary. We will encourage subjects to continue enrollment in the study through follow-up visits, regardless of discontinuation of NIR-TLT.

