4.17.2 Safety Monitoring

Study subjects will undergo frequent clinical assessments including depressive scores, concomitant medications, adverse events, and serious adverse events and unexpected device events will be recorded from study entry to completion. In addition, clinicians should monitor the safety of subjects by frequently asking them about their comfort during treatment delivery.

If skin erythema occurs, treatment will be discontinued. Patients will be instructed to contact the principal investigator of the study site or a member of his or her staff at any time between visits regarding adverse events or worsening of symptoms. If at any study visit, the subjects' clinical status significantly worsens from baseline (operationalized as the clinical global impression severity score, CGI-S, of 6 or greater) or if a subject develops active suicidal intent and/or plan, based on the C-SSRS scale and/or the clinical interview, the subject will be referred to the treating doctor to start an antidepressant medication or make appropriate changes in the treatment regimen. If the subject were considered to be in imminent danger as a result of suicidality, he/she would be discontinued from the study and referred to appropriate clinical treatment (see 4.9 Termination).

The two site principal investigators ([name], PI) will have bi-weekly conference calls (which will include all study staff); during these conference calls, they will discuss all adverse event reports to identify any safety concerns, based on such concerns, they may decide to temporarily discontinue study enrollment, modifications to the study protocol or terminate the study.

In addition, a Data and Safety Monitoring Board (DSMB), composed of at least 3 members not directly involved in the study, will review the SAEs annually. The research assistants responsible for data collection and storage will be aware of and comply with all regulatory requirements related to adverse events. In the event that a patient becomes ill or injured as a direct result of study participation, medical care will be provided. All adverse events (and device events) will be tracked to resolution and reported to the MGH or NKI IRB as serious in the event that:

Transcranial Near Infrared Laser Therapy in Subjects with Major Depressive Disorder: A Laser Dosing Study.

1. Not anticipated and possibly study-related (same report as SAE) or

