4.19 Subject Disposition Criteria

4.19.1 Withdrawal from the Study

Each subject and the investigator reserve the right at any time to terminate a subject's participation in the clinical investigation.

Possible reasons for withdrawal or removal from the study may include:

Transcranial Near Infrared Laser Therapy in Subjects with Major Depressive Disorder: A Laser Dosing Study.

1. The subject voluntarily withdraws consent.
2. The subject was ineligible according to the inclusion and exclusion criteria of the study.
3. The subject develops an adverse event that would not allow continuation in the study.
4. The subject has an adverse event that, in the opinion of the investigator, warrants withdrawal from the study. Pthera LLC must be notified within two business days.
5. The subject and/or the investigator make the decision that the subject should withdraw from the study.
6. Subject to death of participant.
7. Positive pregnancy test during eligibility procedures.
8. The subject misses one of the 3 scheduled sessions per week and it is not possible to make it up before the end of the week. When a subject withdraws or is withdrawn from the study, the following will be performed, if possible, at the study termination (exit) visit:
 - HAM-D-17
 - QIDS-C
 - CGI
 - C-SSRS
 - ADVERSE EVENT FORM
 - Concomitant Medication Form
 - ASQ (self-assessment)
 - SAFTEE-SI (self-assessment)
 - SDQ (self-assessment)

For all subjects who prematurely withdraw from the study, the date and reason for withdrawal will be documented.

4.19.2 *Loss of Follow-up*

If a center is unable to contact a subject or if the subject fails to appear for a visit, three documented telephone calls should be made, followed by a certified letter (or its equivalent, such as an e-mail). The certified letter should detail the need for the subject to appear for a visit, the center's failed attempts to contact the subject, and that failure to contact the center will cause the subject to be withdrawn from the study.

If the certified letter is returned to the center as undeliverable or the letter is delivered but the subject does not communicate with the center and no further contact is made with the subject or the subject's caregiver, then the subject will be considered lost to follow-up with the subject and suspended from the study. All attempts to contact the subject will be documented.

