6.4.1 Security Monitoring

Study subjects will undergo frequent clinical assessments including depressive scores, concomitant medications, adverse events, and serious adverse events, and unexpected device events will be recorded from study entry to completion. In addition, clinicians should monitor a subject's safety by frequently asking them about the subject's comfort during treatment delivery.

If skin erythema occurs, treatment will be discontinued. Patients will be instructed to contact the study site principal investigator or a member of his or her staff at any time between visits regarding adverse events or worsening symptoms. If at any study visit, the subjects' clinical status significantly worsens from baseline (operationalized as Clinical Global Impression Severity Score, CGI-S, of 6 or greater) or if a subject becomes actively suicidal with intent and/or plan, as per On the C-SSRS scale and/or clinical interview, the subject will be referred to the treating doctor to start an antidepressant medication or make appropriate changes in the treatment regimen. If the subject were considered to be in imminent danger as a result of suicidality, he/she would be discontinued from the study and referred to appropriate clinical treatment (see Section - 4.9 Termination).

The site will have bi-weekly conference calls with a designated Pthera LLC study monitor (which will include study RA's); During these conference calls, they will discuss all adverse event reports to identify any safety concerns, based on such concerns, they may decide to temporarily discontinue study enrollment, modifications to the study protocol or terminate the study.

In addition, a DSMB, consisting of at least 3 members not directly involved in the study and not employed by Pthera LLC, will review SAE quarterly. Research assistants responsible for data collection and storage will be aware of and comply with all regulatory requirements related to adverse events. In the event that a patient becomes ill or injured as a direct result of study participation, medical care will be provided. All adverse events (and device events) will be tracked to resolution and reported to the DSMB as serious in the event that they were not anticipated and possibly related to the study (same report as SAE) or meet any of the following criteria, any:

- (1) fatal event,
- (2) immediate life-threatening event,
- (3) event of permanent or substantial disability,

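### Exclusion 9 bars a candidate only when suicidal intent and plan are both present, a looser threshold than the intent and/or plan at which the protocol refers participants during the study

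*Protocol*

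**What the plan says.** Four parts of the protocol set or describe a threshold for suicidality.

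- **Entry.** Exclusion 9 (section 1, Exclusion Criteria): "Active suicidal or homicidal ideation (both intent and plan are present), as determined by C-SSRS screening". Section 4.9.1 has eligibility decided on the full list of inclusion and exclusion criteria.
- **Referral during the study.** Section 4.17.2 sends the participant to the treating doctor to start or adjust antidepressant treatment "if a subject develops active suicidal intent and/or plan, based on the C-SSRS scale and/or the clinical interview". Section 6.4.1 repeats the rule: "if a subject becomes actively suicidal with intent and/or plan". Section 4.9.4 words it a third way, without saying whether intent, plan or both is meant: "if they become actively suicidal according to the C-SSRS scale, the subject will be referred to their treating doctor".
- **Removal.** Referral does not mean removal. Section 4.9.4 says "Such subjects may or may not be terminated from the study, depending on the severity of symptoms", and 4.17.2 makes discontinuation mandatory only at a higher level: "If the subject were considered to be in imminent danger as a result of suicidality, he/she would be discontinued from the study".
- **Stated safeguard.** Section 4.20.1, on the risk of worsening depression and suicidality, says the risk is reduced by selecting only people without active suicidal ideation at screening. It does not mention intent or plan.

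The Table of Assessments places the C-SSRS at V0 and again at V1. Section 4.9.2 lists it among the data collected before the laser session: "Safety data: SAFTEE-SI (self-assessed), C-SSRS, adverse events and concomitant medication form".

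**The concern.** An entry rule may differ from a monitoring rule. One would normally expect entry to be at least as strict, because a candidate can be turned away before any exposure to the study. Here entry is the more permissive of the two, and the protocol gives no reason. Someone with suicidal intent and no plan, or a plan and no stated intent, passes exclusion 9. The same clinical state arising after entry is serious enough, by the protocol's own monitoring sections, to call for a start or change of antidepressant treatment.

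What is at stake is patient safety at the entry decision and consistent application across sites. Staff have one term, active suicidality, with one definition in exclusion 9, another in 4.17.2 and 6.4.1, and none in 4.9.4. The entry threshold also matters because 4.9.1 lets candidates on antidepressants taper and stop before the baseline visit.

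A separate, minor slip sits in the same sentence. Exclusion 9 has homicidal ideation determined by the C-SSRS, while 4.10 describes that scale as covering suicidal ideation and behavior.

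**Working it through.** The protocol states no figure on this point, so the check compares the rules.

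**Step 1: is there another barrier at entry?** The 8 inclusion and 15 exclusion criteria in section 1 were read for any other mention of suicidality. There is none. Exclusion 9 alone decides the matter.

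**Step 2: apply each rule to each state.** Intent (yes/no) by plan (yes/no) gives 2 × 2 = 4 states. Exclusion 9 needs both. The rule in 4.17.2 and 6.4.1 needs at least one.

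| State | Exclusion 9 (both) | Severity covered by 4.17.2 and 6.4.1 (either or both) |
|---|---|---|
| Neither | eligible | not referred |
| Intent only | eligible | referred |
| Plan only | eligible | referred |
| Both | barred | referred |

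Exclusion 9 bars 1 of 4 and the referral rule covers 3 of 4. The difference, 3 − 1 = 2, is the two states with only one element. These are counts of logical states, not of people.

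**Step 3: what happens to such a person at V1?** The C-SSRS is repeated at V1 before the first session. Section 4.17.2 speaks of a subject who develops the state and 6.4.1 of one who becomes actively suicidal. Two readings are open:

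- If the words mean only a new state, someone who enters with intent only and stays the same is neither excluded nor clearly caught by the trigger.
- If they cover any state found at a visit, the same person is eligible at V0 and referable at V1.

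The text does not settle which applies. The entry threshold is the looser one on both readings.

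**Step 4: compare with 4.20.1.** Taken plainly, no active suicidal ideation is stricter than exclusion 9. It is also at least as strict as the referral rule, because it would turn away active ideation with neither intent nor plan.

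**Step 5: room for more screen failures.** Section 4.6 provides subject numbers 01 to 150 to allow for selection failures and drop-out before randomization, and 112 are to be randomized: 150 − 112 = 38.

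**The case against.** The strongest reply is that entry and referral do different jobs. Referral is not removal, 4.9.4 lets referred subjects stay, and a person can coherently be both eligible and referable. That stands as far as it goes. A reader might infer that the protocol admits people whom it would then have to withdraw; it does not, because mandatory discontinuation is tied to imminent danger. What remains is that the looser threshold is at entry and is unexplained.

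Second, the monitoring sections describe a state that develops, and the CGI-S trigger in the same sentence is tied to worsening from baseline. This stands. A reader might infer that a candidate with intent only must trip the referral trigger at V1; the wording allows that reading but does not require it.

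Third, 4.20.1 may only be summarizing exclusion 9, whose parenthesis could be a definition of active ideation. This is possible, so a flat contradiction between the two is not claimed. But if the parenthesis is the definition, it conflicts with 4.17.2 and 6.4.1, which attach the same term to intent and/or plan.

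Fourth, other oversight exists: a psychiatric evaluation at V0, the C-SSRS at V1, discontinuation for imminent danger, and a general withdrawal route in 4.19.1, "The subject and/or the investigator make the decision that the subject should withdraw from the study". These are real protections and limit the consequence. Apart from the V0 evaluation they act after entry, and several rest on judgment; none corrects the written criterion.

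Finally, the count of states assumes that intent and plan are recorded separately. Section 4.10 lists both among the items tracked but does not show how each is scored. The intent-only and plan-only states are therefore taken from the wording of the rules.

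**Conclusion.** The point holds as a mismatch between the entry rule and the referral rule, and it should be fixed. Exclusion 9 leaves two of the four intent and plan states eligible at a severity that 4.17.2 and 6.4.1 refer. On a plain reading it also falls short of the safeguard described in 4.20.1. The conclusion rests on the wording of these sections and on the absence of any other suicidality criterion.

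Its limits are equally clear. The documents give no frequency of intent-only or plan-only candidates at screening, so no number of affected participants can be stated. Nothing supports a claim of harm specific to the sham arm or of an effect on the efficacy estimate. There is no conflict with the rules on who stays in the study. Whether a state already present at entry would trigger referral at V1 is unclear, and that ambiguity is itself worth removing. The homicidal-ideation wording is a minor point and adds no weight to the main one.

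**What to change.** 1. Reword exclusion 9 to *active suicidal ideation with intent and/or plan on the C-SSRS or clinical interview at screening*. To match 4.20.1 literally, the sponsor could instead exclude any active suicidal ideation. Either closes the gap.
2. In 4.9.4, define actively suicidal by the same intent and/or plan standard.
3. Leave 4.17.2, 6.4.1 and 4.20.1 as they are. Rewriting 4.20.1 to intent and/or plan could loosen the stricter selection statement there.
4. Have homicidal ideation judged in the psychiatric evaluation at V0 instead of by the C-SSRS.

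The cost is wording in two places, exclusion 9 (which takes in item 4) and 4.9.4, within a protocol amendment. No assessment is added, since the C-SSRS and the psychiatric evaluation already take place at V0. A few more screen failures are possible. The 38 subject numbers beyond 112 are already meant for such losses, though the protocol does not say how many of them other causes will use.
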